4.3 Statistical Design and Power

A power convention of .80 and for an alpha level of .05 was chosen for evaluating the multilevel model for the proposed site level outcomes (Aim 1) and for the individual level outcomes (Aim 2 and Aim 3). The minimally detectable effect size (MDE) was estimated using Monte Carlo simulation with 1000 replications in *Mplus* 8.5. An advantage of the Monte Carlo simulation approach is the ability to estimate parameter bias, standard errors, and coverage of confidence intervals.

Figure 4.3.1 Phase II Study Design and Expected Sample Sizes by Unit of Analysis

Aim 1 Analyses

Converting the Odds Ratio from the site level preliminary studies and the per capita outcomes Cohen's d ranged from .45 to .60, medium effects. The primary outcome for Aim 1 will be the number of Latinx tested specified as a generalized linear multilevel Poisson model for the count model and as a general linear model for the per capita proportional measures. For Aim 1 analyses, the unit of analysis is the number of total events nested within site. Across the continuing Phase I and the proposed Phase II testing events, there will be a total of 24 events per month for a total of 11 months (264 events).

As an illustration of total number tested, formally, the primary generalized linear model will be the following:

$$\text{Level 1: } E(\text{Test Count}) = \lambda \\ \text{Log}[\lambda] = \beta_0 + \beta_1(\text{Historical Week}) + r$$

$$\text{Level 2: } \beta_0 = \gamma_{00} + \gamma_1(\text{Location Contrast}) \dots \gamma_2(\text{Site Characteristics}) + u_0 \\ \beta_1 = \gamma_{10} + u_1$$

$$\text{Mixed Model: } \text{Log}[\lambda] = \gamma_{00} + \gamma_{01}(\text{Location Contrast}) + \gamma_{02}(\text{Site Characteristics}) + \gamma_{10}(\text{Historical Week}) + u_0 + u_1 + r$$

Where
the
expected
count of
Latinx
tested

represented as $\log \lambda$ is regressed on level 1 historical calendar week β_1 and the effect of the site-location outreach contrast γ_1 is estimated at level 2 as location type effect, controlling for socio-demographic census characteristics of each site γ_2 . Nested models will be compared and evaluated for over or under dispersion, zero-inflation, and normality for the linear mixed model estimating per capita Latinx tested.

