Aim 1 Power. To illustrate power, MDE was estimated for proportion of Latinx tested per capita Latinx population with 1000 replications. One advantage of *Mplus* is the ability to specify events per month according to the design in which 10 census-located sites from Phase 1 will be conducting 20 events per month; and in the other study arm, 4 events per month will be conducted via community partner-located sites. Additionally, the group contrast for location type is simulated according to the clustering design with the appropriate allocation (mean = .42 and variance = .25). Residual variance of number of tested Latinx was specified at .7 for level 1 and .5 for level 2 in order to estimate an intra-class correlation (ICC) of .40, a conservative parameter reflecting the site level ICC from the preliminary analyses ranging from .24 to .37 for the related Latinx testing outcomes described in the preliminary studies section. Covariate parameters were entered with and effect size (ES) of .30 for historical week, and .19 for site characteristics at level 2 with .91 coverage. Models showed that the study is powered .81 to minimally detect an ES of .50, a medium effect.

Aim 2 and Aim 3 Analyses

Both Aim 2 and Aim 3 analyses will focus on the individual unit of analysis. Aim 2 will evaluate whether Phase II implementation fidelity of the *Promotores de Salud* health intervention will improve testing, reduce vaccination hesitancy, and increase vaccine acceptance and health literacy. Aim 3 will focus on the social determinants of pre-post change in the likelihood of vaccination, repeated tested for those unvaccinated, and reduced vaccine hesitancy. Both Aims will be specified as within-intervention group pre-post change. In general, we will estimate pre-post linear mixed models for vaccine hesitancy and generalized linear mixed models for increased testing counts and vaccine acceptance.

Using vaccination as an outcome, both Aims 2 and 3 are formally represented as a multilevel Bernoulli logistic model predicting the likelihood of vaccination:

$$\begin{aligned} \text{Level 1: } \text{Prob}(\text{Vaccine}=1) &= \Phi \\ \text{Log}[\Phi/(1-\Phi)] &= \beta_0 + \beta_1(\text{BL Vaccine Status}) + \beta_2(\text{Social Determinants}) + \beta_3(\text{Historical Week}) + r \end{aligned}$$

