$$\begin{aligned} \text{Level 2: } \beta_0 &= \gamma_{00} + \gamma_1(\text{Fidelity of Implementation}) + \gamma_2(\text{Location Contrast}) \dots \gamma_n(\text{Site Charateristics}) + u_0 \\ \beta_1 &= \gamma_{10} + u_1 \\ \beta_2 &= \gamma_{20} + u_2 \\ \beta_3 &= \gamma_{30} + u_3 \end{aligned}$$

$$\text{Mixed Model: } \text{Log}[\Phi/(1-\Phi)] = \gamma_{00} + \gamma_{01}(\text{Fidelity}) + \gamma_{02}(\text{Location Contrast}) + \gamma_{03}(\text{Site Characteristic}) + \gamma_{10}(\text{BL Vaccine Status}) + \gamma_{20}(\text{Social Determinants}) + \gamma_{30}(\text{Historical Week}) + u_0 + u_1 + u_2 + u_3 + r$$

Where the probability of getting vaccinated Φ is regressed on level 1 baseline vaccine status β_1 , which then estimates the change in vaccine status from pre- to post-*Promotores*. Aim 2 fidelity of implementation is then estimated at level 2 as γ_1 controlling for location type and site level characteristics. Aim 3 social determinants are estimated at level when shown here as β_2 .

Aims 2 and 3 Power. For the multilevel model addressing aims 2 and 3, based on our preliminary Phase I data, we expect a total of 1650 survey participants over 11 months (200 tests per month via census-located events and 100 tests per month in partner-located events, for a total of 300 tests/month, with a 50% enrollment rate into the survey \times 11 months). For the one-month follow-up we anticipate a 50% retention rate. For a total of 825 pre-post participants. Power was estimated using a two-level Monte Carlo simulation, with the ability to model pattern missingness via both location approaches. To be conservative a retention rate was estimated at .50 for the established Phase I location approaches which will include a higher frequency of events, and a retention of .40 was estimated as the missing data pattern for Phase II partner-located; moreover, the proportion of missing data patterns were specified using the proportional design allocation and an ICC of .30 for individual testing outcomes. The proposed study is powered .81 to detect a MDE of .32 for fidelity of implementation at level 2, and is powered .83 to detect an MDE of .11 for social determinant variables at level 1 with .92 coverage.

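### The Aim 1 location contrast sets census sites carried over from Phase I against a Phase II partner-located arm, so it cannot be read as an effect of location type alone

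*SAP*

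**What the plan says.** All SAP references are to section 4.3, Statistical Design and Power.

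- **Arms (Aim 1 Power).** The two arms are described thus: "10 census-located sites from Phase 1 will be conducting 20 events per month; and in the other study arm, 4 events per month". The second arm consists of partner-located sites, and their number is not stated.
- **Phase labels (Aims 2 and 3 Power).** The assumed follow-up retention differs by location approach. For the census-located approach: "a retention rate was estimated at .50 for the established Phase I location approaches which will include a higher frequency of events". The figure for the second approach is lower, and here the phase label changes: "a retention of .40 was estimated as the missing data pattern for Phase II partner-located".
- **Pooling (Aim 1 Analyses).** Events are counted "Across the continuing Phase I and the proposed Phase II testing events", at 24 per month for 11 months.
- **Model (Aim 1 Analyses).** The expected count of Latinx people tested is regressed on historical calendar week at level 1, with a site-specific slope. The location contrast enters at level 2 with census socio-demographic characteristics of the site, and its coefficient is interpreted as the location type effect. The displayed model has no term for phase, time since a site's first event, or earlier testing at the site.
- **Assignment.** The SAP text does not say how sites came to be census-located or partner-located. The Protocol (section C) randomizes sites, 18 to 18, to Promotores or services as usual. It says sites are determined with county public health agencies and mentions no location contrast.

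**The concern.** Randomization does not protect this comparison. Every census-located site has a Phase I history, and the other arm is the Phase II approach. Any difference that comes with phase falls on the location coefficient: familiarity built up in Phase I, demand already met, or a slow or busy start at sites that have just opened. Built-up familiarity would favor the census arm and used-up demand the partner arm, so even the sign of the bias cannot be read from the planned output.

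This matters because the location contrast is the Aim 1 effect that the SAP models and powers, and the planning figures already expect the arms to differ. The Aims 2 and 3 power section assumes 200 tests per month at census-located events and 100 at partner-located events. With 20 and 4 events per month, that is 200/20 = 10 and 100/4 = 25 tests per event. If a gap of that kind appears, the planned analysis would credit it to location type and could not show how much belongs to phase.

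**Working it through.** **1. The SAP's design figures.** 24 events × 11 months = 264, as stated: 20 × 11 = 220 census-located and 4 × 11 = 44 partner-located. The variance components give an ICC of .5/(.5 + .7) = .417, against the stated .40.

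**2. Can the model's terms separate phase from location?**
- *Phase.* All 10 census-located sites are Phase I. If all partner-located sites are Phase II, as the labels suggest, a phase indicator equals the location indicator at every site, and only the sum of the two effects can be estimated.
- *Calendar week.* Both arms are planned over the same 11 months. In a given week both have the same calendar value, whatever their earlier history.
- *Site-specific slope.* Within a site, age is calendar week minus a constant, so this term can follow a site's own growth or decline. It does not remove a systematic difference in level between arms.
- *Census socio-demographics.* These describe residents, not earlier testing at the site.

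**3. Illustration of size (assumed inputs).** The contrast has mean .42. Read as a share of sites, this implies 10 × .42/.58 ≈ 7 partner-located sites, or 10 × .58/.42 ≈ 14 if .42 is the census share. With m partner-located sites:

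Var = (.5 + .7/22)/10 + (.5 + .7/(44/m))/m

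- m = 7: .0532 + .0873 = .1405, SE .375
- m = 14: .0532 + .0516 = .1048, SE .324

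With no true location effect and a phase or maturity difference δ, the two-sided 5% test rejects with probability 1 − Φ(1.96 − δ/SE) + Φ(−1.96 − δ/SE):

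| δ (assumed) | m = 7 | m = 14 |
|---|---|---|
| .2 | 8% | 10% |
| .3 | 13% | 15% |
| .5 | 27% | 34% |

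On the count scale, an assumed change of 2% to 5% per month of operation and an assumed 6-month age gap give a spurious rate ratio of exp(.12) = 1.13 to exp(.30) = 1.35, or 0.89 to 0.74 in the other direction.

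**4. Would a site-age covariate solve it?** Age = calendar week − opening week. If partner-located sites open together at week 0 and census-located sites opened together c weeks earlier, then age = c + week − c × (partner indicator) for every event. Intercept, location, week and age are exactly collinear: four columns, rank 3. The identity also holds for Phase I events, so adding them does not help. If opening dates are staggered within arms the term can be fitted, but at a cost. With 7 partner-located sites and a 26-week gap (both assumed), the location SE grows about 5-fold for an 8-week spread of opening dates and somewhat over 2-fold for a 20-week spread.

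**5. Would a start-up indicator?** An indicator for the first 13 weeks since a site's first event is not collinear with the other terms (rank 4 of 4). Under the same assumptions with common opening dates, the location SE goes from .375 to .378 with Phase I opening events included, and from .376 to .388 without them.

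**The case against.** The strongest reply is that nothing in the SAP says the partner-located sites are new. In the phrase "established Phase I location approaches which will include a higher frequency of events", the adjective describes an approach to choosing locations, not individual sites. Phase II partner-located may mean a new way of placing events in communities already served. The Protocol already worked with community organizations, planned 36 sites and included events funded by the state health authority. This stands. A reader might infer complete confounding with site age, but the documents show only that all census-located sites come from Phase I and that the two approaches carry different phase labels.

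A reader might also infer that the arms differ in prior outreach. The SAP does not say what outreach either set of communities received, and usual county and community outreach is the Protocol's comparator, so that is not established either.

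Some of the record is also out of view. Figure 4.3.1 is not shown, the preliminary studies section is not among the supplied text, and the displayed model is introduced as an illustration. Site selection may be described elsewhere. That would help interpretation, but it would not change how the written model reads the coefficient.

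Finally, the SAP also calls the term an outreach contrast, which could mean a bundled strategy. A bundle is a fair target, but a site's Phase I history is not part of the strategy being compared.

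**Conclusion.** The point holds as one of interpretation. The Aim 1 location coefficient comes from a comparison not described as randomized, in which location type goes with phase. The terms in the model do not separate the two. Confounding with site maturity follows only to the extent that partner-located sites are new, which remains an inference from the labels.

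Size and direction are unknown. The rejection rates and rate ratios above rest on assumed differences, trends, gaps and site counts. They show that a plausible difference could matter, not that bias of that size is present. The documents do not support a stronger claim, whether that every partner-located site is newly opened or that the estimate is biased by a known amount or in a known direction. What they do support is that the planned output could not justify attributing a difference to location type alone.

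**What to change.** 1. In Aim 1 Analyses, replace the location-type reading of the coefficient with a non-randomized comparison of Phase I census-located sites and Phase II partner-located sites, not attributable to location type alone. State how sites came to each location type and whether the partner-located sites had held earlier events.
2. Add a sensitivity analysis with a start-up-period indicator, for example the first 3 months since a site's first event. Use Phase I opening-month events where they are held, and report how the location estimate changes.
3. Do not add a linear site-age term unless opening dates vary substantially within each arm, because otherwise it is collinear with calendar week and location.

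The cost is SAP wording, a first-event date for each site, and re-use of Phase I event data where available. The loss of precision from the indicator is small under the assumptions above. The downsides are a more limited Aim 1 conclusion and a partial adjustment. The indicator removes only opening-period differences, and the arms' opening months fall in different calendar periods, so it still leans on the calendar-week term.

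### The SAP's simulations report interval coverage of .91 and .92 without comment; if the intervals are nominal 95%, both are clearly short, and the .83 power for social determinants is not shown to be power at alpha .05

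*SAP*

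**What the plan says.** All of this is in SAP section 4.3. The opening paragraph fixes the error rates: "A power convention of .80 and for an alpha level of .05 was chosen for evaluating the multilevel model". It gives 1,000 replications for the simulations and names as an advantage of the approach "the ability to estimate parameter bias, standard errors, and coverage of confidence intervals". So coverage here means confidence-interval coverage, and it is meant as a check.

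Two coverage values follow.

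- **Aim 1 Power.** The covariate sentence ends "and .19 for site characteristics at level 2 with .91 coverage". The next sentence gives power of .81 for an effect size of .50, with no coverage value.
- **Aims 2 and 3 Power.** The same sentence gives two results: "The proposed study is powered .81 to detect a MDE of .32 for fidelity of implementation at level 2", and then "powered .83 to detect an MDE of .11 for social determinant variables at level 1 with .92 coverage".

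Section 4.3 does not state the nominal interval level, sidedness or an acceptable range for coverage. It gives no bias results and no rejection rates under the null. It names no estimator, degrees-of-freedom method or reference distribution for the site-level tests. The model checks it does plan (dispersion, zero-inflation, normality) concern fit, not interval validity.

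**The concern.** Coverage is the simulation's own test of whether the intervals, and the Wald tests that match them, work at their nominal level. A 95% interval that covers 91 or 92% of the time corresponds to a test whose size may be nearer 8 or 9% than 5%. Power from such a test is not power at alpha .05.

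The .92 stands next to a stated power of .83, so that figure is directly affected. The location contrast (Aim 1) and fidelity (Aim 2) are site-level effects, as is the site-characteristics covariate named just before the .91. The same weakness could therefore affect them, and their stated power of .81 is close to the .80 convention. If it does, the final analysis would report site-level intervals that are too narrow.

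**Working it through.** **Inputs from SAP 4.3.** Alpha .05; 1,000 replications (stated generally and repeated for Aim 1, but not repeated for Aims 2 and 3); coverage .91 and .92; power .81 (Aim 1), .81 (fidelity) and .83 (social determinants). The Aim 1 simulation uses residual variances .7 (level 1) and .5 (level 2), 264 events, 10 census-located sites and an allocation mean of .42.

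**Assumption.** Nominal 95% two-sided intervals.

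**1. Can the .91 be reproduced?** Not strictly, because the text gives neither the number of partner-located sites nor the scale of the effect size. Step 4 gives the nearest check.

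**2. Are .91 and .92 within simulation error of .95?**

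- Monte Carlo SE = √(.95 × .05 / 1000) = .0069, so estimates should mostly fall in .95 ± 1.96 × .0069 = .9365 to .9635.
- (.95 − .91) / .0069 = 5.8; exact binomial lower tail about 1 in 10 million.
- (.95 − .92) / .0069 = 4.4; exact lower tail about 3.5 in 100,000.
- Most favourable rounding: .915 is 5.1 SEs low and .925 is 3.6 SEs low.
- If the intervals were nominal 90%: SE = √(.90 × .10 / 1000) = .0095, and .91 and .92 would be 1.1 and 2.1 SEs above nominal. There would be no shortfall.

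**3. What might .92 mean for the .83?** It depends on the cause.

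- *Standard errors too small.* Coverage of .92 corresponds to a true critical value of 1.751 instead of 1.96 (SE ratio .893). Power .83 adds .954, so the standardised effect is 1.751 + .954 = 2.705. Power at a true 5% test is Φ(2.705 − 1.96) = .77.
- *Bias only.* Coverage of .92 needs a shift of .508 SE. The power becomes Φ(.954 − .508) = .67 or Φ(.954 + .508) = .93, depending on its sign.

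The stated .83 could therefore be too high or too low.

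**4. Is a site-level shortfall plausible?** An allocation mean of .42 with 10 census-located sites fits 24 sites (10/24 = .417) or 17 sites (7/17 = .412). These counts are inferred. Figure 4.3.1 may give the true number but is not shown. Two simulations of the linear Aim 1 model used the SAP's variances and covariate effect of .19: A with 20,000 replications and events spread evenly, B with 3,000 replications and events split 220 to 44.

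| Quantity | 17 sites | 24 sites |
|---|---|---|
| A: ML with z, coverage of contrast / site covariate | .906 / .902 | .921 / .923 |
| B: ML with z, coverage of site covariate | .895 | .918 |
| B: REML with t, coverage of site covariate | .944 | .952 |
| A: power for the contrast at a raw effect of .50 | .35 | .41 |

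Coverage near .91 is what uncorrected intervals give with this few sites, and a small-sample method brings it back to about .95. The same runs do not reproduce the stated power of .81.

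**5. Do few sites explain the level-1 .92?** A linear analogue with 825 participants and ICC .30 gave level-1 coverage of .94 to .97 when slopes did not vary between sites. Few sites alone do not explain it, and its cause is unknown.

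**The case against.** **The level is not stated.** On a 90% reading there is no shortfall. This stands as a condition on the finding. Alpha .05 makes 95% the natural reading, and on either reading the level needs stating.

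**No powered site-level test is shown to under-cover.** This stands. The .91 closes a sentence on covariates, and the .92 follows the level-1 determinants. A reader might infer that the tests of the location contrast and fidelity have inflated type I error, or that their .81 is really well below .80. The documents do not support either inference, because they give no coverage for those effects.

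**The few-sites explanation does not fit every stated figure.** This also stands. In simulation A, power reached .82 only at about 102 sites, where coverage was .941 and .945. No site count tried gave both stated figures, so the SAP's design or effect scale differs from the one assumed. The check shows plausibility, not cause.

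**Power also carries Monte Carlo error.** With 1,000 replications, .81 has an SE of √(.81 × .19 / 1000) = .012. Its margin of .01 over .80 is within that error, so no conclusion is drawn from the margin.

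**Consequence is limited and the text is partial.** The Aim 1 calculation is presented as an illustration: "To illustrate power, MDE was estimated for proportion of Latinx tested per capita Latinx population with 1000 replications". Only section 4.3 is available, it refers to a preliminary-studies section that was not supplied, and Figure 4.3.1 is not shown. Statements about what is absent hold for section 4.3 only. What remains is that section 4.3 reports its own diagnostic at values that look poor and does nothing with them.

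**Conclusion.** The point holds conditionally. If the intervals are nominal 95% and 1,000 replications apply to both simulations, coverage of .91 and .92 is 5.8 and 4.4 Monte Carlo standard errors low. Rounding does not remove the shortfall. The intervals described miss the true value about 8 to 9% of the time, and the .83 for social determinants is not shown to be power at alpha .05.

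For the location contrast and fidelity, a shortfall is plausible because both are site-level effects and sites appear to be few. It is not shown. A reader might also infer that all the stated powers are too high. That does not follow, since the cause of the .92 is unknown and bias could move the .83 in either direction.

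The finding concerns the SAP's Aims 1 to 3. None of these parameters is the randomised comparison of Promotores with services as usual in protocol section C. Correction before analysis is worthwhile and cheap. Confidence is medium, because the nominal level and the number of sites are not stated.

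**What to change.** 1. State the nominal interval level and sidedness, and say which parameters .91 and .92 describe.
2. Pre-specify a small-sample method for site-level effects (location contrast, site characteristics, fidelity): REML with Kenward-Roger or Satterthwaite degrees of freedom for the linear models, and between-within degrees of freedom or a comparable correction for the Poisson and logistic models. This does not by itself deal with the level-1 .92.
3. Re-run the simulation with that method and the planned number of sites. Check bias, the patterned missingness and the random slopes as possible causes of the .92.
4. Report coverage, bias and null rejection rate for each tested effect, and restate the powers (.81, .81, .83) and their detectable effects (.50, .32, .11) from that run, whichever way they move.

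The cost is SAP wording, one simulation re-run, and slightly wider intervals for site-level effects.

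### The Aim 1 power of .81 for an ES of .50 does not follow from the SAP's own inputs if ES is Cohen's d (at most about .55), and on the reading where .81 is reachable the effect is not medium

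*SAP*

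**What the plan says.** SAP section 4.3 sets power and alpha in general terms: "A power convention of .80 and for an alpha level of .05 was chosen". It does not say whether the test is one- or two-sided.

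Under Aim 1 Analyses, events are nested within sites and the location contrast "is estimated at level 2 as location type effect". There are 24 events a month for 11 months, 264 in all. Effects from the preliminary studies are given in Cohen's d: "d ranged from .45 to .60, medium effects".

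Under Aim 1 Power, the layout simulated is "10 census-located sites from Phase 1 will be conducting 20 events per month; and in the other study arm, 4 events per month" at community partner-located sites. The contrast has mean .42 and variance .25. "Residual variance of number of tested Latinx was specified at .7 for level 1 and .5 for level 2", to give an ICC of .40. Covariate effects are .30 for historical week and .19 for site characteristics. The conclusion is "Models showed that the study is powered .81 to minimally detect an ES of .50, a medium effect".

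The readable text gives neither the number of partner sites nor the scale of the ES. Figure 4.3.1, which concerns expected sample sizes, is not reproduced in the copy reviewed.

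**The concern.** A contrast between types of site is limited by the number of sites, not the number of events. Ten sites in one arm, with a large share of the variance between sites, is a small design, and .81 for a half-SD effect looks too high for it.

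This is the only power figure given for Aim 1. It follows preliminary effects of d = .45 to .60 and invites the reader to conclude that an effect of that size would probably be found. If the true power is nearer one half or lower, a null location result would be misread as evidence against a medium effect.

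**Working it through.** **Inputs (SAP section 4.3)**
- Census arm: 10 sites, 20 events a month × 11 months = 220 events, 22 per site.
- Partner arm: 4 events a month × 11 months = 44 events. The number of sites, J, is an assumption, at most 44 (one event each). With 10 census sites, a .42 share fits J = 7 (7/17 = .41) or J = 14 (10/24 = .42).
- Residual variances: .7 (event) and .5 (site); total 1.2; ICC .5/1.2 = .417, close to the stated .40.
- Alpha .05, two-sided assumed.

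**Effect of .50 on three scales (coefficient b)**
- Raw coefficient: b = .500.
- d on the residual SD: b = .50 × sqrt(1.2) = .548.
- d on the full marginal SD: SD² = 1.2 + .30² + .19² + .25b² with b = .50 SD, so SD² = 1.3261/(1 − .0625) = 1.4145 and b = .595.

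**Can .81 be reproduced?** Power of .81 requires SE = b/(1.960 + .878), that is .176, .193 or .210. The SE of the contrast is

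SE = sqrt[(.5 + .7/22)/10 + (.5 + .7/(44/J))/J].

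Whatever J and the number of events, this exceeds sqrt(.5/10) = .224, so no two-sided reading of .50 on these scales reaches .81. Even at that floor, power is .61, .69 or .76.

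**Power for .50 at feasible J, from Φ(b/SE − 1.960)**

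| Partner sites J | SE | Raw | d, residual SD | d, marginal SD |
|---|---|---|---|---|
| 7 | .375 | .27 | .31 | .36 |
| 14 | .324 | .34 | .39 | .45 |
| 44 (ceiling) | .284 | .42 | .49 | .55 |

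Maximum-likelihood simulations with a z test and the site covariate gave .44 to .58 at J = 44, depending on the scale. That test rejected in 6% to 8% of replications with no effect at J = 44, and 9% to 10% at J = 7, so the simulated powers are somewhat inflated.

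**Effect detectable with 80% power** (2.802 × SE, converted to d)

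| J | d, residual SD | d, marginal SD |
|---|---|---|
| 7 | .96 | .83 |
| 14 | .83 | .73 |
| 44 | .73 | .65 |

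All exceed .60. At d = .60 on the residual SD and J = 44, power is .64.

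**If .50 is a standardised level-2 slope**
- The contrast then explains .25 of the between-site variance: b = sqrt[V/(3Vx)]. V is .5, or .5361 with the site covariate. Vx is .25, .42 × .58, or the variance implied by 10 and J sites.
- Power is .59 to .63 at J = 7 and .71 to .75 at J = 14.
- It first rounds to .81 at J between 18 and 34, depending on V and Vx, with b of .82 to .88.
- That b is a d of about .75 to .80 on the residual SD, or from .67 on the marginal SD.

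**If clustering is ignored** (220 against 44 independent events, variance 1.2): power is .79 for raw .50 and .86 for d = .50. This brackets .81 but contradicts the multilevel model.

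**The case against.** The best defence is that the SAP never says .50 is a Cohen's d. It uses ES for the covariate parameters too, and d appears only for the preliminary studies. On a standardised-slope reading a coherent simulation could return about .81. The J range of 18 to 34 is also sensitive to method: a maximum-likelihood z test gave .75 to .78 at 14 partner sites, and .77 to .82 for 24 sites of 11 events each. The latter also totals 264 events but departs from the stated 20/4 monthly split. This stands as far as it goes. A simulation error is not proven, and the J range is approximate. It does not rescue the sentence, because on that reading the medium label fails against the SAP's own d of .45 to .60.

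Other relaxations do not close the gap at d = .50:
- One-sided at 44 partner sites: .55, .61 or .67 on the three scales. One-sided power passes .81 only on the marginal SD with far more partner sites than 44 events allow.
- ICC of .24, the bottom of the preliminary range: .61 at 44 sites.
- The protocol's 18 + 18 sites, which are not the SAP's Aim 1 layout: .57 to .61.

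Figure 4.3.1 may give the sites per arm, so their absence from the text is not held against the plan. The two-sided floor does not depend on that count. The calculation is also introduced as an illustration for the per-capita linear model, but its conclusion is stated for the study.

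**Conclusion.** The concern holds as an either/or. If the ES is Cohen's d, two-sided power for .50 is at most about .55, not .81, and .27 to .45 at the site counts that fit the stated allocation. If it is a standardised slope, .81 is attainable, but for a d of about .67 to .80, which is outside the SAP's medium range. On the stated inputs the effect detectable with 80% power is at least d = .65, above every preliminary effect quoted.

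This rests on a level-2 contrast, 10 census sites, the stated residual variances and a two-sided 5% test. The partner-site count is assumed, from 7 to its ceiling of 44. The random slope for historical week is left out. The finding does not bear on the protocol's randomised comparison of Promotores with usual services.

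**What to change.** State the ES metric and the sidedness beside the power figure, with the sites per arm and events per site (or a pointer to Figure 4.3.1 if it gives them). Rerun the simulation with the contrast at level 2 and a small-sample reference test, such as a Satterthwaite or Kenward-Roger t. The SAP's own reported coverage of .91, against a nominal .95, points the same way, although it is given beside the covariate effects rather than the contrast.

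Replace the sentence with the power for d = .50, or the 80% detectable effect in Cohen's d, from that rerun. If .50 was a standardised slope, say so, give the equivalent d and remove the medium label.

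The cost is one rerun of an existing simulation and one sentence. No sites, participants or analyses are added. The downside is a less favourable stated power or detectable effect.
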